CLINICAL STUDY PROTOCOL

A Sibling Oocyte Study- Comparison of ZyMot™ Microfluidics Device to Density Gradient for Sperm Selection During ICSI

Principal Investigator

[name]

Sponsor

DxNow

[name]

<https://zymotfertility.com/>

Protocol Version

17 March 2021

version DRAFT

s21-00021

NCT04818593

Study Personnel

Principal Investigator

[name]
Email: [contact]

Sub-Investigators

[name]
Email: [contact]

[name]
Email: [contact]

[name]
Email: [contact]

[name]
Email: [contact]

[name]
Email: [contact]

[name]
Email: [contact]

[name]
Email: [contact]

[name]
Email: [contact]

[name]
Email: [contact]

Key Study Personnel:

[name]
Email: [contact]

[name]
Email: [contact]

Synopsis

Primary Objective

The primary objective of this study is to evaluate whether the percentage of good quality embryo formation following ICSI is improved with the use of ZyMot method of microfluidic sperm separation compared to density gradient.

Secondary Objectives

The secondary objectives will be to evaluate:

1. Sperm parameters prior to and following sperm separation with ZyMot compared to density gradient
2. Normal fertilization rates following ICSI comparing sperm separation with ZyMot with density gradient
3. Euploid rates, in the event that PGT-A was performed, following ICSI comparing sperm separation with ZyMot with density gradient
4. Embryo transfer results including:
5. Not pregnant
6. Biochemical pregnancy, defined as BHCG value > 5 mIU/ml without ultrasound evidence of gestational sac within the uterus
7. Clinical miscarriage, defined as loss of a pregnancy following a positive BHCG value and ultrasound revealing presence of a gestational sac within the uterus
8. Clinical pregnancy, defined as positive BHCG with a gestational sac within the uterus
9. Ongoing Pregnancy, defined as a positive BHCG value with ultrasound evidence of intrauterine gestational sac at or past 8 weeks gestation
10. Live birth defined as birth of a baby at 20 weeks or later, showing signs of life, including breathing, beating of the heart, pulsation of the umbilical cord, or definite movement of the voluntary muscles.
11. Ectopic Pregnancy, defined as positive BHCG and presence of pregnancy outside of the uterus.

Study Duration

The study will be completed once 408 oocytes are randomized, which is anticipated to be in approximately 1-2 years.

Study Design

Subjects meeting inclusion criteria will be approached for inclusion into the study and informed consent will be obtained from the patient and the sperm source. Controlled ovarian hyperstimulation will be performed followed by oocyte retrieval as per our standard protocol. On the day of oocyte retrieval, sperm samples will be split into two samples and processed via density gradient (our standard sperm separation technique) and ZyMot (our experimental arm). Sperm parameters will be evaluated pre and post-sperm separation following ZyMot and density gradient. Following oocyte retrieval, the oocytes will be assessed as per our standard fashion. In the event that the oocytes will be inseminated via intracytoplasmic sperm injection (ICSI) and there are 6 or more mature oocytes, half of the oocytes will be inseminated via ZyMot processed sperm and half with sperm processed via density gradient. In the event that there are less than 6 mature oocytes or the insemination technique will be IVF, the oocytes will only be inseminated with sperm processed via density gradient. Additionally, in the event that the sperm sample is insufficient for ZyMot processing (<0.5 million total motile sperm and/or no sperm observed with progressive forward motility), the sperm will not be processed with ZyMot and the patient will be withdrawn from the study.

The primary outcome will be percentage of good quality embryo formation resulting from oocytes inseminated following ZyMot separated sperm compared to density gradient separated sperm. Secondary outcomes will include percentage of euploid embryos in the

event that PGT-A is performed, pregnancy rates, miscarriage rates, live birth rates, and sperm parameters following sperm processing. Decision to transfer an embryo will be made as per our standard protocols regardless of the sperm processing technique.

Study Population

The study population will include patient/sperm donor dyads where all patients over 18 years of age are undergoing controlled ovarian hyperstimulation for IVF with ICSI using ejaculate sperm and having at least 6 mature oocytes retrieved. The sperm source/donor will provide informed consent for the use of their sperm sample in this research study. The relationship of the sperm source will can be the intended father, a known sperm donor in a same-sex couple or a known donor in the case of a single patient. The identity of the donor cannot be anonymous.

Number of Participants

Following power calculation, 408 oocytes will be needed to randomize (see details in the statistics section). The number of patient/sperm source dyads enrolled will depend on the number of oocytes obtained from each patient. The maximum number of subjects will be 68 (in the event that 6 oocytes were obtained from every patient enrolled in the study).

Number of Study Sites

This study will take place at NYU Langone Reproductive Specialists of NY.

Primary Outcome Variables

The primary outcome of our study is to evaluate whether good quality embryo formation is significantly improved with ICSI following sperm separation using ZyMot compared to density gradient.

Secondary and Exploratory Outcome Variables

The secondary objectives will be to evaluate:

1. Sperm parameters prior to and following sperm separation with ZyMot compared to density gradient
2. Normal fertilization rates following ICSI comparing sperm separation with ZyMot with density gradient
3. Euploid rates, in the event that PGT-A was performed, following ICSI comparing sperm separation with ZyMot with density gradient
4. Embryo transfer results including:
 - a. Not pregnant
 - b. Biochemical pregnancy, defined as BHCG value > 5 mIU/ml without ultrasound evidence of gestational sac within the uterus
 - c. Clinical miscarriage, defined as loss of a pregnancy following a positive BHCG value and ultrasound revealing presence of a gestational sac within the uterus
 - d. Clinical pregnancy, defined as positive BHCG with a gestational sac within the uterus
 - e. Ongoing Pregnancy, defined as a positive BHCG value with ultrasound evidence of intrauterine gestational sac at or past 8 weeks gestation
 - f. Live birth, defined as birth of a baby at 20 weeks or later, showing signs of life, including breathing, beating of the heart, pulsation of the umbilical cord, or definite movement of the voluntary muscles.

1.1 Introductory Statement

The primary objective of this study is to evaluate whether the percentage of good quality embryo formation following ICSI is improved with the use of ZyMot method of microfluidic sperm separation compared to density gradient.

2 - Background

2.1 Background/prevalence of research topic

Sperm integrity and function is critical to embryo formation and IVF success rates. Male factor infertility accounts for approximately 1/3 of infertility diagnosis and is the single most common diagnosis for IVF cycles in the US. During an IVF cycle, oocytes retrieved are inseminated with sperm via IVF or ICSI. IVF is the process by which approximately 50,000-100,000 motile sperm are incubated with one or more oocytes, whereas ICSI is the process of selecting and injecting a single sperm into an oocyte. ICSI was originally developed to treat male factor infertility, however, its use has been greatly expanded in ART including insemination of cryopreserved oocytes, previous fertilization failure or poor fertilization results following IVF, unexplained infertility, in vitro maturation, cases of PGT when paternal contamination is of concern, and other clinically relevant indications at the physician's discretion (1). Selection of healthy sperm for use in ICSI is critical to ICSI success. Density gradient is a commonly used method to select sperm for ICSI, which depends on centrifugation, and is the standard of care for sperm processing prior to ICSI in our institution. This technique requires mechanical and chemical processing that can increase oxygen free radical formation, which can cause sperm DNA damage and increase in DNA fragmentation (2, 3). Although conflicting data exists as to whether elevated levels of sperm DNA fragmentation compromises live birth rates in assisted reproductive technology (ART) treatments, some data has revealed that increased sperm DNA fragmentation decreases fertilization rates, decreases progression to good quality embryos, decreases pregnancy rates, and increases miscarriage rates (4-10). Studies have shown elevated levels of sperm DNA fragmentation in infertile males with abnormal semen parameters (11-13), however, interestingly data has revealed that increase levels of DNA fragmentation can also be found in infertile males with normal semen parameters (14).

Separation of sperm with microfluidics prior to ART resembles the physiologic environment that sperm encounters in the female reproductive tract more closely compared to density gradient, and has been proposed to decrease sperm DNA fragmentation. Indeed, separation via ZyMot, a microfluidic technique has been shown to significantly decrease sperm DNA fragmentation compared to the traditional density gradient technique (15). In a non-randomized study with a small sample size enrolling couples with recurrent ART failure and male factor infertility with high sperm defragmentation, outcomes with density gradient versus microfluidic sperm separation using ZyMot were compared and revealed that embryo euploid rates following PGT-A and pregnancy rates were significantly improved with the use of ZyMot (16). A retrospective study evaluating pregnancy rates using ZyMot sperm separation compared to density gradient for intrauterine insemination (IUI) revealed significantly higher ongoing pregnancy rates with use of ZyMot compared to density gradient (17). Additionally, a prospective randomized study evaluating ZyMot sperm separation with the swim up technique for patients undergoing ICSI due to unexplained infertility revealed a significant increase in good quality embryo formation with ZyMot sperm separation, however, this study included a significant proportion of embryos evaluated and transferred at day 3 or 4 as opposed to day 5, which is our standard of care (18).

The aim of our study is to evaluate whether good quality embryo formation is significantly different following ICSI comparing sperm separated using ZyMot with density gradient.

References

1. Practice Committees of the American Society for Reproductive M, the Society for Assisted Reproductive Technology. Electronic address aao. Intracytoplasmic sperm injection (ICSI) for non-male factor indications: a committee opinion. *Fertility and Sterility* 2020;114:239-45.

2.2.1 Device Preclinical Experience

The ZyMot Multi Sperm Separation Device (850µl) is used to prepare motile sperm for use in ART. ZyMot separates motile sperm from the semen based on the motility of the sperm within a microenvironment. The ZyMot Multi sperm separation device has an inlet port for applying the semen sample to the lower sample chamber and an outlet port for collecting the motile sperm from the upper collection chamber. The chambers are separated by a microporous filter or membrane. After incubation at 37C for 30 min, the culture medium containing motile sperm is collected from the outlet port.

The device is made from Polymethylmethacrylate, borosilicate glass, flash-spun high-density polyethylene fibers. The devices are gamma radiation-sterilized devices with a sterility assurance level (SAL) of 10⁻⁶. They are individually packaged and for single-use only.

This device has been FDA approved for our proposed use (see attached).

2.2.2 Device Clinical Experience

Separation via ZyMot has been shown to significantly decrease sperm DNA fragmentation compared to the traditional density gradient technique (15). In a non-randomized study with a small sample size enrolling couples with recurrent ART failure and male factor infertility with high sperm defragmentation, outcomes with density gradient versus microfluidic sperm separation using ZyMot were compared and revealed that embryo euploid rates following PGT-A and pregnancy rates were significantly improved with the use of ZyMot (16). A retrospective study evaluating pregnancy rates using ZyMot sperm separation compared to density gradient for intrauterine insemination (IUI) revealed significantly higher ongoing pregnancy rates with use of ZyMot compared to density gradient (17). Additionally, a prospective randomized study evaluating ZyMot sperm separation with the swim up technique for patients undergoing ICSI due to unexplained infertility revealed a significant increase in good quality embryo formation with ZyMot sperm separation, however, this study included a significant proportion of embryos evaluated and transferred at day 3 or 4 as opposed to day 5, which is our standard of care (18).

3 - Rationale/Significance

3.1 Problem Statement

Commonly used methods for separating and processing sperm prior to ICSI involves mechanical and chemical processing such as density gradient separation. Density gradient sperm separation can increase sperm oxygen free radicals and DNA fragmentation. Sperm oxygen free radicals and DNA fragmentation can adversely affect sperm quality which can adversely affect ART success rates. Sperm separation via microfluidics separates sperm in a more physiologic fashion and has been shown to decrease DNA fragmentation as compared to the density gradient.

3.2 Purpose of Study/Potential Impact

We intend to evaluate whether formation of high-quality embryos following ICSI are improved with ZyMot microfluidic sperm separation compared to density gradient. Potential impact of the study could be that good quality embryo formation is improved with ZyMot compared with density gradient, which could have a positive impact on ART success rates.

3.3.1 Potential Risks

Potential risks of the study include the possibility that good quality embryo formation may not be improved with the use of ZyMot or may be inferior compared to density gradient. Inferior embryos could negatively impact the ability of the embryo to lead to yield a liveborn fetus. To our knowledge, existing literature has not revealed any detrimental effect to the quality of embryo formation with the use of the ZyMot device. Additionally, enrollment in the study can incur possible psychological distress due to study participation.

Procedures to limit psychological distress will be a thorough informed consent process, ability to discuss with any participating provider questions related to the study, and ability to withdraw enrollment at any point prior to insemination of the oocytes.

3.3.2 Potential Benefits

Potential benefit to study enrollment could be that good quality embryo formation is improved following sperm separation with ZyMot compared to density gradient, which could improve the participant's ART success rates.

4 - Study Objectives

4.1 Hypothesis

We hypothesize that the percentage of good quality embryo formation following ICSI will be improved with sperm separated via ZyMot compared to density gradient.

4.2 Primary Objective

The primary objective of this study is to evaluate whether the percentage of good quality embryo formation following ICSI is improved with the use of ZyMot method of microfluidic sperm separation compared to density gradient.

4.3 Secondary Objectives

The primary objective of this study is to evaluate whether the percentage of good quality embryo formation following ICSI is improved with the use of ZyMot method of microfluidic sperm separation compared to density gradient.

The secondary objectives will be to evaluate:

1. Sperm parameters prior to and following sperm separation with ZyMot compared to density gradient
2. Normal fertilization rates following ICSI comparing sperm separation with ZyMot with density gradient
3. Euploid rates, in the event that PGT-A was performed, following ICSI comparing sperm separation with ZyMot with density gradient
4. Embryo transfer results including:
 - a. Not pregnant
 - b. Biochemical pregnancy, defined as BHCG value > 5 mIU/ml without ultrasound evidence of gestational sac within the uterus
 - c. Clinical miscarriage, defined as loss of a pregnancy following a positive BHCG value and ultrasound revealing presence of a gestational sac within the uterus
 - d. Clinical pregnancy, defined as positive BHCG with a gestational sac within the uterus
 - e. Ongoing Pregnancy, defined as a positive BHCG value with ultrasound evidence of intrauterine gestational sac at or past 8 weeks gestation
 - f. Live birth defined as birth of a baby at 20 weeks or later, showing signs of life, including breathing, beating of the heart, pulsation of the umbilical cord, or definite movement of the voluntary muscles.
 - g. Ectopic Pregnancy, defined as positive BHCG and presence of pregnancy outside of the uterus.

As per our standard of care, patients will be contacted by embryology staff via phone after their expected due to date for their pregnancy outcome. Pregnancy outcomes will be recorded in the patient's medical record.

5 - Study Design

5.1 General Design Description

This study will be a randomized sister oocyte (oocytes from the same patient within the same cycle) study at a single academic institution. By randomizing sister oocytes, we will eliminate any potential confounding variables.

5.1.1 Study Date Range and Duration

The anticipated study duration is anticipated to be approximately be 1-2 years following initiation of subject recruitment.

5.1.2 Number of Study Sites

This study will take place at NYU Langone Reproductive Specialists of NY.

5.2 Outcome Variables

5.2.1 Primary Outcome Variables

The primary objective of this study is to evaluate whether the percentage of good quality embryo formation following ICSI is improved with the use of ZyMot method of microfluidic sperm separation compared to density gradient.

Good quality embryos will be defined as blastocyst stage embryos on day 5 or day 6 of culture with an overall quality grade of good or fair.

5.2.2 Secondary and Exploratory Outcome Variables

The secondary outcomes will be to evaluate:

1. Sperm parameters prior and following sperm separation with ZyMot compared to density gradient.
2. Sperm parameters that will be evaluated are sperm concentration, percent motility, and grade of forward progression.
3. Normal fertilization rates following ICSI comparing sperm separation with ZyMot to density gradient. Normal fertilization will be defined as visualization of exactly two pronuclei between 16-18 hours post-insemination.
4. Euploid, aneuploid, and mosaic rates in the event that PGT-A was performed following ICSI comparing sperm separation with ZyMot to density gradient. PGT-A biopsy samples will be sent to and analyzed by Cooper Genomics.
5. Euploid embryo will be defined as 46XX or 46XY. Mosaic rates will be defined as presence of euploid and aneuploid cells and be reported as high or low mosaic. High mosaicism will be defined as embryos having 41 - 80% aneuploid cells, whereas, low mosaicism will be defined as 20 - 40% aneuploid cells.
6. Embryo transfer results including:
 - a. Not pregnant
 - b. Biochemical pregnancy, defined as BHCG value > 5 mIU/ml without ultrasound evidence of gestational sac within the uterus
 - c. Clinical miscarriage, defined as loss of a pregnancy following a positive BHCG value and ultrasound revealing presence of a gestational sac within the uterus
 - d. Clinical pregnancy, defined as positive BHCG with a gestational sac within the uterus
 - e. Ongoing Pregnancy, defined as a positive BHCG value with ultrasound evidence of intrauterine gestational sac at or past 8 weeks gestation
 - f. Live birth defined as birth of a baby at 20 weeks or later, showing signs of life, including breathing, beating of the heart, pulsation of the umbilical cord, or definite movement of the voluntary muscles.
 - g. Ectopic Pregnancy, defined as positive BHCG and presence of pregnancy outside of the uterus.

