6.1.2 Device administration and schedule

Patient/sperm source dyads enrolled in the study and meeting inclusion criteria will have their sperm sample prepared prior to, or near the time of, oocyte retrieval. Semen parameters will be recorded prior to separation. Semen will be split and separated via ZyMot and density gradient.

Density gradient will be performed as follows:

- Density gradient centrifugation will be performed using a one-layer preparation of 90% Isolate (Irvine Scientific) in 15 mL conical tubes. Semen will be layered over 1 mL of gradient and then centrifuged for 15 min at 300xg. The supernatant will be removed and discarded. The sperm pellet will be washed by mixing with Multipurpose Handling Medium Complete (Irvine Scientific) and centrifuging the sample for 5 min at 400xg. After the wash, the supernatant is removed and discarded and the pellet is re-suspended in culture medium (Continuous Single Culture-NX Complete, Irvine Scientific), assessed for sperm parameters, and held at room temperature until insemination.

ZyMot separation using the Multi (850 uL) microfluidic separation device will be performed as follows:

- 850 uL of untreated semen will be directly deposited into the inlet port of the ZyMot™ Multi device, followed by placement of 750 uL culture medium (Continuous Single Culture- NX complete, Irvine Scientific) in the outlet port and throughout the upper collection chamber. The device will then be incubated in a humidified 37C CO2 incubator for 30 minutes. During incubation, the healthiest and most motile sperm will swim through the microporous filter and into the upper collection chamber, where they will be recovered via the outlet port. 500 uL of the sperm sample will be removed and placed in a separate tube for analysis and insemination.
- After sperm processing, sperm parameters will be evaluated and recorded for each preparation, including sperm concentration, percent motility, and grade of forward progression. The density gradient preparation results will be recorded as Sample 1 in the electronic medical record (eMR) system gamete sheet. The ZyMot preparation results will be recorded as Sample 2 in the eMR system gamete sheet.

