6.4.3.2 Secondary Objectives Analyses

Sperm parameters following ZyMot and density gradient sperm separation, as well as Euploid rates in the event that PGT-A was performed following ICSI comparing sperm separation with ZyMot to density gradient, will be assessed using the paired t-test, Wilcoxon signed rank test, or a generalized linear mixed model (GLMM). A random subject-specific intercept and an unstructured correlation structure will be used to account for within-subject correlation between rates between the two groups. Data will be reported as least squares means with corresponding 95% confidence intervals.

Pregnancy outcomes will be assessed using McNemar's test. The difference in good quality blastocyst development rate and pregnancy outcomes between the ZyMot and density gradient separation groups will also be analyzed separately using a conditional logistic regression model with generalized estimating equations to account for both correlation between observations from the same patient and the size of the cohort of eggs from each patient.

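### Post-preparation sperm concentration is tested between methods while the density-gradient volumes are left unspecified, so a difference cannot be read as separation performance

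*Combined protocol and SAP*

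**What the plan says.** Section 5.2.2 of the combined protocol and SAP defines the sperm outcome: "Sperm parameters that will be evaluated are sperm concentration, percent motility, and grade of forward progression". Section 6.1.2 gives the matching recording instruction: "After sperm processing, sperm parameters will be evaluated and recorded for each preparation, including sperm concentration, percent motility, and grade of forward progression". Neither list names a volume, a total count or a yield.

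Section 6.1.2 describes the two preparations in unequal detail.

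- **ZyMot.** Every volume is given: "850 uL of untreated semen will be directly deposited into the inlet port", "followed by placement of 750 uL culture medium" into the outlet port and collection chamber, and after incubation "500 uL of the sperm sample will be removed and placed in a separate tube for analysis and insemination".
- **Density gradient.** The only volume given is that of the gradient: "Semen will be layered over 1 mL of gradient and then centrifuged for 15 min at 300xg". After the wash, "the supernatant is removed and discarded and the pellet is re-suspended in culture medium", with no volume stated. The section says that the semen is split but not in what proportions.

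For the analysis, section 6.4.3.2 takes "Sperm parameters following ZyMot and density gradient sperm separation" and allows a paired t-test, a signed rank test or a mixed model. None of these is adjusted for volume. Section 6.4.1 sets significance at p < 0.05.

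**The concern.** Concentration is a count divided by a volume. If the volume in one arm is a laboratory choice that the plan does not state, a paired test of concentration mixes that choice with what the method does. If the choice is systematic, the test can be significant in either direction when both methods recover the same fraction of sperm. The objective sets one separation method against another, so readers would take such a result as a statement about the methods.

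The stake is limited to one of three parameters in one secondary objective. Sperm parameters are, however, the only study data from dyads who have fewer than six mature oocytes or who go to IVF insemination (sections 6.1.2, 6.3.4 and 6.3.7).

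**Working it through.** The plan states no figure on this point, so there is none to reproduce. The check is dilution arithmetic.

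**Inputs from section 6.1.2:** ZyMot semen input 0.85 mL, collection medium 0.75 mL, volume removed 0.50 mL.

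**Assumed inputs, because the documents give none:** density-gradient semen volume Vin and re-suspension volume Vf.

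**Formula.** Let C be the semen concentration and f the fraction of input sperm recovered. Then

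concentration after preparation = f × C × (Vin / Vf).

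Both preparations come from the same semen, so C cancels in a paired comparison. Vin / Vf does not.

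**ZyMot factor.** With sperm spread through the medium in the collection chamber, 0.85 / 0.75 = 1.133. Drawing off 500 uL of that medium does not change its concentration.

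**Density gradient to ZyMot ratio at equal f, with 0.85 mL of semen in both:**

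| Assumed Vf (mL) | 0.85 / Vf | Ratio (÷ 1.133) |
|---|---|---|
| 0.25 | 3.40 | 3.00 |
| 0.50 | 1.70 | 1.50 |
| 0.75 | 1.133 | 1.00 |
| 1.00 | 0.85 | 0.75 |

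The ratio is 1 only where Vf happens to equal the ZyMot medium volume.

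**Sensitivity to the ZyMot assumption.** If all recovered sperm are taken to lie in the 0.50 mL removed, the ZyMot factor is 0.85 / 0.50 = 1.70 and the four ratios become 2.00, 1.00, 0.67 and 0.50. The direction still depends on Vf.

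**Sensitivity to input.** Hold Vf at 0.50 mL and use the 1.133 factor. Assumed density-gradient inputs of 0.50, 0.85 and 2.15 mL then give ratios of (0.50/0.50)/1.133 = 0.88, (0.85/0.50)/1.133 = 1.50 and (2.15/0.50)/1.133 = 3.79.

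**What a volume-adjusted measure does.** Multiply concentration by recovered volume and divide by the input count.

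- Density gradient: f × C × (Vin/Vf) × Vf / (C × Vin) = f. Both volumes drop out.
- ZyMot, counting the 0.50 mL removed: f × C × (0.85/0.75) × 0.50 / (C × 0.85) = f × 0.50/0.75 = 0.667 f.

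On this usable-yield scale, equal recovery into the medium gives a fixed ratio of 1 / 0.667 = 1.5, whatever the density-gradient volumes. That 1.5 reflects the third of the medium that the protocol leaves in the device, so it is a real difference in sperm available for injection. Counting all 0.75 mL would give 1.0 but would describe recovery into the chamber. The analysis section must therefore say which ZyMot volume counts.

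**The case against.** A reader might infer that the two preparations do have different volumes, that density gradient receives whatever semen is left over, or that the concentration test measures dilution as much as separation. The documents support none of these. They say only that the semen is split and the pellet re-suspended. Density gradient is the site's standard technique, so laboratory practice may fix its volumes even though the protocol does not state them. The 0.25 mL final volume in the section 6.1.2 table is a minimum for IVF eligibility, not a preparation volume. The supportable statement is that the density-gradient volumes are unspecified and not standardised in the plan.

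It can also be said that the objective asks about sperm parameters, not recovery, and that the concentration of the sample as prepared is a fair description of what the embryologist works with. That stands, and it is why raw concentration should still be reported. It does not justify a significance test between methods that readers will take as a comparison of performance.

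Lastly, volume is partly in view already. The IVF-eligibility table uses initial and final volume, section 6.1.7 applies a total motile count to the initial ejaculate, and the recording list in section 6.1.2 is not exhaustive. Some volumes may therefore be recorded anyway. The outcome list in section 5.2.2 is closed, however, and section 6.4.3.2 uses no volume, so recording alone would not change the test.

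**Conclusion.** The point holds for sperm concentration only. As written, the paired test cannot separate a difference in recovery from a difference in the ratio of input to final volume, and the plan leaves that ratio open for density gradient. With equal recovery, 0.85 mL of semen in both, and sperm spread through the ZyMot medium, the apparent density-gradient to ZyMot ratio runs from about 3.0 to 0.75 as the assumed re-suspension volume goes from 0.25 to 1.0 mL. These figures show how sensitive the comparison is; they do not predict the trial's result. Simple dilution does not alter percent motility or progression grade, and neither the primary endpoint nor the 408-oocyte sample size uses concentration. This is a minor but worthwhile improvement.

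**What to change.** Record the semen input volume and the final recovered volume for each preparation. In section 6.4.3.2, make the between-method comparison on usable motile-sperm yield:

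(concentration × motility × recovered volume) / (input motile count).

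Take the 500 uL removed as the recovered volume for ZyMot and the re-suspended volume for density gradient. Input motile count is semen input volume × initial concentration × initial motility. Use the signed rank test, which the section already lists, so that preparations with zero motile sperm stay in the analysis. Report raw post-preparation concentration descriptively, and leave percent motility and progression grade as planned.

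The cost is two recorded volumes per preparation and one changed sentence in the analysis section. The change should be made before enrolment, because volumes not noted at preparation may be impossible to recover later.
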